Treatment failure will be defined as any crossover from one treatment to another due to patient's respiratory distress and discomfort. To be more specific, switch of gas flow from 40L/min to 60L/min, crossover from either NHF group to standard practice (Venturi mask) or need for more advanced respiratory support such as non-invasive ventilation or invasive mechanical ventilation, inability to reverse FiO_2 and/or gas flow escalation above initial settings within 48 hours of its initiation. Escalation reversal will be defined as return to initial (or lower) FiO_2 and/or gas flow for ≥ 4 hours.

Inclusion criteria will be: Cardiac ICU adult patients > 18 years after elective or urgent cardiac surgery having passed a successful Spontaneous Breathing Trial (SBT) with T-piece and $\text{FiO}_2=0.6$. A successful SBT will have to fulfil the following criteria^{31, 32, 33} respiratory rate: 12-29 breaths/min, $\text{SpO}_2 > 92\%$, $\text{PaCO}_2 < 45\text{ mmHg}$, heart rate <120/min, and systolic arterial pressure of 90-160 mmHg while receiving norepinephrine at a rate of 0.00 $\mu\text{g}/\text{kg}/\text{min}$ to 0.15 $\mu\text{g}/\text{kg}/\text{min}$. The most important inclusion criterion is residual respiratory impairment at the end of SBT defined as $\text{PaO}_2/\text{FiO}_2 < 200 \text{ mmHg}$ while receiving $\text{FiO}_2=0.6$. The decision to extubate under these specific conditions will be made by the attending physicians.

The exclusion criteria will comprise: 1) Obstructive Sleep Apnea Syndrome supported by a continuous positive airways pressure device, 2) preoperative diagnosis of Chronic Obstructive Pulmonary disease, 3) patients already tracheostomized, 4) do not resuscitate status, 5) Glasgow Coma Scale score <13, 6) Insufficient knowledge of Greek Language , and 7) any visual or hearing impairment.

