Secondary: 1] Successful maintenance of an SpO₂ of >92% and a respiratory rate of 12-29 breaths/min at the specified time points of follow-up; the term "successful" corresponds to the absence of any escalation of respiratory support above its initially specified level for each one of the Study groups and the Control group; 2] PaO₂/FiO₂ at the specified time points of follow-up; 3] Any use of accessory respiratory muscles at the specified time points of follow-up; and 4] Patient comfort as regards dyspnea, and patient tolerance of NHF support according to a VAS score.

Additional: 1] Length of cardiothoracic ICU stay; 2] Length of hospital stay; 3] ICU and in-hospital mortality; and 4] Adverse events (e.g. hypoxemia and/or need for re-intubation, arrhythmias such as atrial fibrillation, occurrence of delirium, epileptic seizures, surgical re-exploration due to bleeding, ICU readmission, chest wound infection), and any patient discomfort/intolerance related to NHF.

Sample Size and Power Analysis

The proposed sample size is based on a formal power calculation, i.e. an *apriori* power analysis, which is an efficient method of controlling statistical power before a study is actually conducted; for power analysis, G*Power 3 software was used.⁴⁴ We predict a treatment failure rate of 15% in the 2 Study groups (10% in Study group 1 and 20% in Study group 2) and a failure rate of 51% in the Control group. The predicted NHF-to-control treatment failure ratio of 0.29 corresponds to the lower limit of the 95% confidence interval (CI) of a previously determined "NHF vs. Control" odds ratio for support escalation.²⁵ For alpha=0.05 and power=0.80, 63 patients (n=21 per group) will be required. However, we cannot exclude a potential risk for dropouts and/or missing data. To compensate for such a risk, we propose the ultimate enrolment of 99 patients (i.e. n=33 per group), in order to achieve an alpha value of 0.05, a power of 0.96, and a "safety margin" of 57% as regards possible dropouts and/or missing data. The predicted study enrollment rate is 40-50 patients per year.

Interim Analysis and Data Monitoring

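### The 15% versus 51% planning rates are supported by equating their risk ratio (0.29) with the lower confidence limit of an odds ratio; the odds ratio they imply is 0.17

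*Combined protocol and SAP*

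**What the plan says.** All the planning figures are in the section Sample Size and Power Analysis. For the NHF arms it says "We predict a treatment failure rate of 15% in the 2 Study groups (10% in Study group 1 and 20% in Study group 2"); control failure is put at 51%. The only evidence offered for this contrast is the next sentence: "The predicted NHF-to-control treatment failure ratio of 0.29 corresponds to the lower limit of the 95% confidence interval (CI) of a previously determined" NHF versus control "odds ratio for support escalation", with a citation to an earlier study. That study's point estimate, upper limit and control rate are not given.

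From these rates, at alpha 0.05 and power 0.80, the section concludes that "63 patients (n=21 per group) will be required". It then raises enrolment to 99 (33 per group) to cover dropouts and missing data, "in order to achieve an alpha value of 0.05, a power of 0.96", and a margin "of 57% as regards possible dropouts and/or missing data".

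The Methods section defines the endpoint: "Treatment failure will be defined as any crossover from one treatment to another" because of respiratory distress and discomfort. It goes on to list the switch from 40 to 60 L/min, the move from NHF to Venturi mask, the need for non-invasive or invasive ventilation, and escalation that cannot be reversed within 48 hours.

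**The concern.** The 0.29 is a quotient of two proportions, and it is set equal to a limit on the odds-ratio scale. The two scales nearly agree only when events are rare. At a 51% control rate they are far apart, and for a protective effect the odds ratio is further from 1 than the risk ratio. Reading an odds ratio of 0.29 as a risk ratio of 0.29 therefore makes the planned effect larger than the cited evidence implies. The limit used is already the end of the interval most favourable to NHF, so the planned effect lies outside the interval.

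At stake is how the trial's power will be read. A null result would be judged against a stated power of 0.96 when the one piece of evidence cited does not reach the effect on which that power depends.

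**Working it through.** **Inputs.** Failure 15% NHF (10% and 20% by arm) and 51% control; ratio 0.29; 63 and 99 patients; alpha 0.05 (Sample Size and Power Analysis). Allocation 1:1:1, so NHF to control is 2:1 when pooled (Randomization procedure). Two-tailed P values, and Fisher's exact test for percentages (Statistical Analysis Plan). The test behind the power calculation is not named, so three are shown.

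**1. Reproducing the plan's figures from 15% and 51%.**

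| Method (two-sided 0.05) | Power at 63 | Power at 99 |
|---|---|---|
| Pooled NHF vs control, Fisher, exact enumeration | 0.817 | 0.952 |
| Pooled NHF vs control, z test | 0.851 | 0.963 |
| Three-group chi-square, 10/20/51%, 2 df, w = 0.393 | 0.804 | 0.948 |

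Pooled Fisher gives 0.794 at 60 patients (40 vs 20), so 63 is the first multiple of three from there to reach 0.80. The three-group chi-square also first reaches 0.80 at 63. For the z test at 66 vs 33, the pooled rate is (2 × 0.15 + 0.51)/3 = 0.27. The null SE is √[0.27 × 0.73 × (1/66 + 1/33)] = 0.0947. The SE under the alternative is √[0.15 × 0.85/66 + 0.51 × 0.49/33] = 0.0975. Power = Φ[(0.36 − 1.96 × 0.0947)/0.0975] = Φ(1.79) = 0.963. The stated sizes and powers follow from the stated rates.

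**2. Which ratio is 0.29?**
- Risk ratio: 0.15/0.51 = 0.294.
- Odds ratio: (0.15/0.85)/(0.51/0.49) = 0.1765/1.0408 = 0.170.

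The 0.29 is the risk ratio. On the scale of the cited limit, the planned effect is 0.17.

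**3. What an odds ratio of 0.29 means at 51% control.** NHF odds = 0.29 × 1.0408 = 0.3018. NHF failure = 0.3018/1.3018 = 23.2%. The risk ratio is 0.232/0.51 = 0.455.

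**4. Power if that limit were the planning basis (23.2% vs 51%).**

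| Method | Power at 63 | Power at 99 |
|---|---|---|
| Pooled Fisher | 0.536 | 0.764 |
| Pooled z | 0.602 | 0.792 |
| Three-group, both NHF arms 23.2% (w = 0.280) | 0.499 | 0.704 |
| Three-group, 10-point gap kept: 18.2/28.2/51% (w = 0.293) | 0.538 | 0.746 |
| Three-group, 1:2 ratio kept: 15.5/30.9/51% (w = 0.311) | 0.590 | 0.797 |

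The z test at 99, with pooled rate (2 × 0.232 + 0.51)/3 = 0.325, gives Φ[(0.278 − 1.96 × 0.0998)/0.1013] = Φ(0.81) = 0.792.

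**5. Sensitivity to the control rate.** The cited study's control rate is not in the documents. A 15% NHF rate has an odds ratio of 0.29 only if control failure is 37.8% (odds 0.1765/0.29 = 0.6085; 0.6085/1.6085 = 0.378). Over assumed control rates from 37.8% to 65%, with the odds ratio held at 0.29, power at 99 is 0.65 to 0.78 (pooled Fisher) or 0.71 to 0.82 (pooled z).

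**The case against.** The strongest reply is that the plan predicts its rates and says only that their ratio corresponds to the limit. It does not say that 15% was derived from it. The sizes and powers then stand whatever the sentence says, and every figure in steps 4 and 5 needs an odds ratio of 0.29 to be the true basis. This is right as far as it goes: those power figures are conditional, and the sponsor may have another reason for 15%. But no other reason is given, and the correspondence claimed is false on the plan's own numbers.

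A reader might infer more than the documents support in three ways.

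- **That the sample size is miscalculated or the trial underpowered.** Step 1 shows otherwise for the stated rates, and the true rates are unknown.
- **That power 0.96 and a 57% margin for the same 99 patients are contradictory.** The section prints both 0.80 at 63 and 0.96 at 99, and 57% is exactly 36/63, the margin over the required number. It is not offered as a tolerable loss among the 99. At most it deserves a note: 0.96 applies if all 99 are evaluable, and losing the 36 spare patients (36/99 = 36%) returns power to about 0.80.
- **That support escalation is a different endpoint from treatment failure.** The Methods definition itself counts need for advanced support and the 40 to 60 L/min switch, so the two overlap substantially. How the cited study defined escalation is not in the documents, so the size of any mismatch cannot be judged.

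**Conclusion.** The concern holds for the sentence that justifies the rates. A risk ratio of 0.29 is presented as matching an odds-ratio limit, whereas the planned rates imply an odds ratio of 0.17, beyond the limit most favourable to NHF. This needs no outside source, because the section prints both rates, the 0.29 and the name of the measure.

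The fault is in the support for the rates, not in the sample-size arithmetic. Its possible size, if the odds-ratio limit is the basis and control failure is 51%, is power of about 0.70 to 0.80 instead of 0.96 at 99 evaluable, and about 0.50 to 0.60 instead of 0.80 at 63. Where in those ranges it falls depends on the test and on the split between the NHF arms. It should be fixed, but it does not invalidate the design.

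**What to change.** Keep 99 patients and reword the Sample Size and Power Analysis section.

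**Preferred.** Delete the sentence equating 0.29 with the odds-ratio limit. Give a direct basis for the 10%, 20% and 51% failure rates under the definition of treatment failure in Methods. The statements on 63 and 99 patients can then stay.

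**If the odds-ratio limit is kept as the basis.** State that at 51% control it implies about 23% NHF failure and that it is the most favourable limit. Give power with all 99 evaluable as about 0.70 to 0.80 (pooled NHF vs control: Fisher 0.76, z 0.79; three-group chi-square 0.70 to 0.80), and about 0.50 to 0.60 at 63. Withdraw the statements that 63 patients give 0.80 and that 99 give 0.96 with a 57% margin, since they cannot stand beside a 23% rate. Present these figures as a planning illustration: the plan does not specify a pooled Fisher comparison for treatment failure, and its Statistical Analysis Plan assesses the group effect by Cox regression.

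**Cost.** Wording only, with no change to enrolment, design or analysis. The price is the work of finding a direct basis for the rates or, on the second route, a less favourable power statement with little or no reserve for losses.

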At 1 year following study start, an interim analysis will be conducted by Drs. [name] (Senior Consultant in Intensive Care Medicine, First Department of Intensive Care Medicine, University National and Kapodistrian University of Athens Medical School, Evangelismos General Hospital, Athens, Greece) and [name] (Senior Consultant, Department of Cardiac Surgery, Evangelismos General Hospital, Athens, Greece). The analysis will be focused at evaluating and confirming 1) the safety of the study protocol (including any reported adverse events); 2) the applicability of the study protocol (including an assessment of the achieved level of adherence to the specified investigational interventions); 3) the completion of the attached study forms as mandated by the study protocol; and 4) the safety of the electronically stored patient data. Actions related to the

aforementioned points 1-4 may be undertaken at the discretion of the aforementioned study-independent Colleagues at any time point throughout the conduct of the current study. Data quality and completeness will also be evaluated by the aforementioned study-independent Colleagues after the completion of the study.

Statistical Analysis Plan

Analyses will be performed according to intention-to-treat principle. Distribution normality will be determined by Kolmogorov Smirnov test. Continuous variables will be presented as mean \pm SD or median (IQR). Qualitative variables will be presented as number (percentage). Percentages will be compared by Fisher's exact test.

The effect of group on treatment failure will be assessed using multivariable Cox regression. Hazard ratios and respective 95% confidence intervals will be determined for group, EuroSCORE II (which includes age and gender as risk factors), body mass index, cardiopulmonary bypass time, and duration of postoperative sedation and pre-extubation assisted and spontaneous breathing.

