$\text{SpO}_2 > 92\%$, and respiratory rate within 12- 20 breaths/min will be assessed as binary outcomes (i.e. maintenance vs. no maintenance of SpO_2 /respiratory rate above/within the aforementioned limits without escalation of support above initial level) Logistic regression models will be fitted using group, time, and group*time interaction as explanatory variables. Changes in oxygenation, VAS comfort scale score, and non-outcome follow-up variables (i.e. PaCO_2 , arterial blood lactate, hemoglobin concentration, hemodynamic variables, temperature, and vasopressor support) will be analysed by using linear mixed models analyses with group, time, and group*time, as fixed factors, and "patients" as random factor. Dependent variables with skewed distributions will be log-transformed. The Bonferroni correction will be applied on the P values of pairwise comparisons.

Two-tailed P values will be reported. Statistical significance will be accepted at 0.05. Analyses will be conducted using SPSS version 21 or any subsequent version (IBM corporation, Armonk NY).

Importance of the study

The early use of NHF in post-extubated cardiac surgery patients may potentially assist them in achieving a faster recovery by providing higher and more stable levels of humidified and warmed oxygen while supporting the respiratory effort through positive airway pressures. This could also be associated with a reduction in the risk for postoperative pulmonary complications. This study may also help in determining the best level of initial NHF support in cardiac surgery patients with postoperative hypoxemia.

Study Funding Statement

The AIRVO™ 2 (Fisher & Paykel Healthcare, Auckland New Zealand) device (with built in flow generator) is already available at our institution. Regarding disposables, we estimate a total cost of 90 Euro per patient (heated humidifier, 60 Euro; Nasal prongs, 15 Euro; compatible opti flow circuit, 15 Euro. The maximum cost of disposables is estimated at 5940

Euro (+24% value added tax). This cost will be covered by the Special Account for Research Funds, University of Athens Medical School, Athens, Greece. The current study will not cause any financial burden to Evangelismos Hospital.

Doctoral Thesis

This study corresponds to the Doctoral Thesis of [name].

References (updated 14/09/2018)

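### Fisher's exact test is valid but conservative for arm-versus-arm percentages at 33 per group; Boschloo's test would recover some power at the same 5% level

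*Combined protocol and SAP*

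**What the plan says.** The Statistical Analysis Plan gives one general rule for proportions: "Percentages will be compared by Fisher's exact test". It adds "Two-tailed P values will be reported" and "Statistical significance will be accepted at 0.05". After the mixed-model text it adds "The Bonferroni correction will be applied on the P values of pairwise comparisons", without giving the number of comparisons or saying whether the rule covers the Fisher tests. It does not say whether the Fisher tests compare all three groups at once or pairs of groups.

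Two outcomes have their own models. The group effect on treatment failure, the primary outcome, goes to multivariable Cox regression. Maintenance of SpO2 and respiratory rate goes to logistic regression. The section names SPSS as the software.

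Under Sample Size and Power Analysis the plan says "For alpha=0.05 and power=0.80, 63 patients (n=21 per group) will be required", then "we propose the ultimate enrolment of 99 patients (i.e. n=33 per group", with "a power of 0.96" at that size. The predicted failure rates are 10% (60 L/min), 20% (40 L/min), 15% for the two NHF groups together, and 51% for control.

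**The concern.** Fisher's test conditions on both margins of the 2×2 table: the arm sizes and the total number of events. In this trial the design sets the arm sizes but not the event total. With 33 per arm, few P values are attainable for a given event total, so the rule P ≤ 0.05 rejects much less often than 5% of the time when the arms do not differ. The unused error rate is lost power.

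Boschloo's test takes Fisher's P value as its statistic but finds the cut-off from the two fixed arm sizes, maximising the error over the unknown common event rate. It rejects every table that Fisher rejects, and some more, while staying at or below 5%.

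The outcomes that depend on the blanket sentence are crude failure percentages, accessory-muscle use, ICU and in-hospital mortality, re-intubation, ICU readmission and other adverse events. Several of these concern safety. For them, a conservative test makes a real difference between arms easier to report as no difference.

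**Working it through.** **Inputs.** From the plan: 33 per group, 1:1:1 allocation, two-sided 0.05, and failure rates of 10%, 20%, 15% (NHF pooled) and 51%. Assumed, because the documents give no adverse-event rates: 3% versus 15% and 5% versus 20%.

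**Method.** List every table (x, y) with x events of n₁ and y of n₂. Compute the two-sided Fisher P for each, summing the hypergeometric probabilities no larger than that of the observed table. Then

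rejection probability = Σ 1[P(x, y) ≤ c] · Bin(x; n₁, p₁) · Bin(y; n₂, p₂).

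With p₁ = p₂ this is the true size; otherwise it is power. Fisher uses c = 0.05. Boschloo uses the largest c whose size, maximised over the common rate, is at most 0.05.

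**Step 1: the plan's own figures.** Fisher's test for pooled NHF (15%) against control (51%), two to one:

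- 20 control versus 40 NHF: 79.4%
- 21 versus 42: 81.7%, so 21 per group (63 in all) is the smallest size that reaches 0.80, as stated
- 33 versus 66: 95.2%, against the stated 0.96

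The stated sample size can therefore be reproduced with Fisher's test itself. A three-group chi-square on 10%, 20% and 51% fits about as well (80.5% and 94.8%), so the documents do not settle which was used.

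**Step 2: true size at 33 versus 33, nominal 5%.**

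| Common event rate | Fisher | Boschloo |
|---|---|---|
| 5% | 0.2% | 0.9% |
| 10% | 1.2% | 2.6% |
| 20% | 2.4% | 4.0% |
| 30% | 2.5% | 4.6% |
| 50% | 3.6% | 3.9% |

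The maximum over all rates is 3.56% for Fisher and 4.85% for Boschloo. Boschloo's cut-off is a Fisher P of about 0.077.

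**Step 3: power at 33 versus 33, unadjusted 5%.**

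| Rates | Fisher | Boschloo | Gain (points) |
|---|---|---|---|
| 20% v 51% | 0.689 | 0.763 | 7.5 |
| 10% v 51% | 0.946 | 0.969 | 2.3 |
| 10% v 20% | 0.116 | 0.158 | 4.3 |
| 5% v 20% (assumed) | 0.293 | 0.383 | 9.0 |
| 3% v 15% (assumed) | 0.188 | 0.298 | 11.0 |

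To match Boschloo at 33 per arm for 20% versus 51%, Fisher needs 40 per arm, which is (40 − 33) × 3 = 21 more patients over three arms. Two tables show where a conclusion would change: 0/33 versus 5/33 (Fisher P = 0.053) and 1/33 versus 7/33 (P = 0.054). Both lie above 0.05 and below Boschloo's cut-off.

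**Step 4: other settings.**

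- Pooled NHF versus control (66 versus 33), 15% versus 51%: 95.2% with Fisher, 95.7% with Boschloo.
- Three-group Fisher-Freeman-Halton test, 33 per group: true size 2.1% at a 5% event rate, and 3.9% to 4.6% at rates of 10% to 50%.
- If Bonferroni covers three pairs (0.05/3 = 0.0167, an assumption): maximum size 0.92% for Fisher and 1.56% for Boschloo; power for 20% versus 51% is 0.505 and 0.589.
- If losses cut the arms to 21: power for 20% versus 51% is 0.427 with Fisher and 0.546 with Boschloo.

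**The case against.** The strongest reply is that nothing here is wrong. Fisher's test is standard, prespecified and valid, and choosing between conditional and unconditional exact tests is partly a matter of taste. That stands, so this is a point about efficiency and not about error control.

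Three stronger readings are tempting, and the documents do not support them.

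- A reader might infer that the primary analysis loses power. The group effect on treatment failure is assigned to Cox regression, and the SpO2 and respiratory-rate outcome to logistic regression. The failure rates above therefore illustrate only the crude comparison of percentages.
- A reader might infer that the sample size is undermined. Step 1 shows that 63 patients is reproducible with Fisher's test for pooled NHF versus control, so its conservatism may already be allowed for. In that comparison Boschloo adds about half a point.
- A reader might infer that every percentage is tested at 0.2% to 3.6%, with Bonferroni making it worse. The plan does not say that the Fisher tests are pairwise, and a three-group test loses less. Nor does it tie Bonferroni to these tests or state the number of pairs.

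The gain is also limited where power is weakest. The comparison of the two flows moves only from 12% to 16%. At a 5% event rate Boschloo's true size is still 0.9%. For 1% versus 5% (assumed), power moves only from 0.4% to 1.7%.

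What survives is narrower: where two arms are compared on an unmodelled percentage, Boschloo is at least as powerful as Fisher at every pair of rates, under the same 5% ceiling.

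**Conclusion.** This is a cheap improvement, not a fault in the plan. For arm-versus-arm percentages at 33 per group, Fisher's test leaves much of the 5% unused. Boschloo's test recovers about 2 to 7 points of unadjusted power at the protocol's predicted failure rates, and about 9 to 11 points at the assumed adverse-event rates. The benefit falls on crude failure percentages and on outcomes without a model.

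The size of the gain rests on pairwise testing, full arms of 33, and common event rates of 5% to 50% for the error range; below 5% Fisher's true size is lower still. The 11-point figure depends wholly on the assumed 3% versus 15%. The 60 versus 40 L/min comparison of failure percentages remains uninformative with either test.

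**What to change.** Replace the sentence on percentages with wording such as: *Two-group comparisons of percentages will use Boschloo's unconditional exact test (two-sided), reported with the risk difference and its confidence interval. Three-group comparisons of percentages will use the Fisher-Freeman-Halton exact test.* Amend the software sentence so that a package providing Boschloo's test may be used alongside SPSS. Make both changes before outcome data are analysed.

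The cost is two edited sentences and no extra patients or data. The downside is that the test may have to be run outside SPSS; the documents do not say whether SPSS offers it. The risk difference with its interval is useful in its own right, because the plan promises no effect estimate for these percentages.

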Studies applying NHF immediately after extubation in cardiac surgery patients revealed better oxygenation and less need for advanced methods of respiratory support compared to conventional oxygen devices^{25,26}, and similar results compared to noninvasive ventilation²⁷. However, Zochios et al,²⁸ summarized all the available up to date data of NHF compared to conventional oxygen devices and non-invasive ventilation in patients undergoing cardiothoracic surgery and they did not find any further benefit by NHF use. The aforementioned discordant results could be explained by the differences in the studied populations and NHF flow settings. The proposed initial flow rate differs among the studies, with some authors^{2,4} suggesting initial lower flows (35-40 L/min) that will be better tolerated by the patients and others suggesting initial maximal flows (60 L/min) to rapidly relieve dyspnea and prevent muscle fatigue.^{29,30}

Aim

The primary goal of the study is to evaluate the efficacy of NHF versus conventional oxygen systems as regards treatment failure (as defined below) and respiratory parameters [respiratory rate, PaO_2 / (fraction of inspired oxygen) FiO_2 , peripheral oxygen saturation (SpO_2), use of accessory muscles, and dyspnea and comfort as regards the technique of respiratory support by using a visual analogue scale (VAS) after the extubation of cardiac surgery patients. An additional major goal of the study is to compare two different initial NHF flows of 60 L/min and 40 L/min, intensive care unit (ICU) Length of Stay, Hospital Length of Stay, rates of ICU re-admission and re-intubation and any other respiratory / non-respiratory complications and adverse events. The rate of failure of the initial treatment will be determined as the primary study outcome.

Methods

This is a prospective, non-blinded, randomized study in post-extubated cardiac surgery patients. The study population will consist of three patient groups: The first group (Study Group 1) will include patients on NHF with initial settings of $\text{FiO}_2=0.6$ and gas flow=60L/min. The second group (Study Group 2) will include patients on NHF with initial settings of $\text{FiO}_2=0.6$ and gas flow=40L/min. In the third group (control group) all patients will receive oxygen therapy according to the standard practice of our cardiac ICU department, i.e., Venturi mask with $\text{FiO}_2=0.6$ and flow of 15 L/min.

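### Respiratory rate, a respiratory parameter named in the Aim, is tested only as in or out of a band and is left out of the linear mixed models, at a loss of power.

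*Combined protocol and SAP*

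**What the plan says.** The Aim sets out to judge efficacy "as regards treatment failure (as defined below) and respiratory parameters [respiratory rate", where the rate stands in a list with PaO2/FiO2, SpO2, accessory muscle use, dyspnea and comfort. The Detailed description counts a lower respiratory rate among the effects of NHF. Patient monitoring and data collection schedules a baseline reading within 30 minutes of extubation, then readings at 1, 2 and 4 hours and four-hourly to 48 hours. That is 1 + 2 + 12 = 15 readings, 14 of them after baseline.

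Under Statistical Analysis Plan, "respiratory rate within 12- 20 breaths/min will be assessed as binary outcomes". A reading counts as maintained only if it is "above/within the aforementioned limits without escalation of support above initial level". The model is a logistic regression on group, time and their interaction. Linear mixed models with the same fixed terms, and patient as random factor, are kept for "Changes in oxygenation, VAS comfort scale score, and non-outcome follow-up variables". The last group is spelled out as PaCO2, "arterial blood lactate, hemoglobin concentration, hemodynamic variables, temperature, and vasopressor support". Respiratory rate is in neither part of that list. The only other provision that reaches it is the general rule for presenting continuous variables as mean or median, which is descriptive.

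Outcome measures defines the same secondary outcome with "a respiratory rate of 12-29 breaths/min at the specified time points of follow-up". The upper limit is therefore 29 there and 20 in the Statistical Analysis Plan.

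**The concern.** The expected effect is a downward shift in a number. The plan turns that number into yes or no before testing it, and gives the fuller analysis to haemoglobin and temperature, which it calls non-outcome variables. Oxygenation and comfort, which stand beside respiratory rate in the Aim, also get a mixed model. No reason is given for the difference.

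Two things are at stake. One is power on a question the Aim poses. The other is direction: both bands have a lower limit of 12, so an arm whose rates fall can gain readings at the top of the band and lose them at the bottom. The no-escalation condition blurs the picture further. Under Management of respiratory support, escalation is triggered by SpO2, so a patient with an in-band rate can be scored as not maintained for an oxygenation reason.

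**Working it through.** **The plan's own figure.** None is given for respiratory rate. The stated power (0.80 at N=63, 0.96 at N=99) is for treatment failure. A three-group chi-square with rates 10%, 20% and 51% (w = 0.393, 2 df) gives 0.804 and 0.948. Comparing 15% with 51% at 2:1 gives 0.851 and 0.963. The figure is broadly reproduced and is not in question here.

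**Inputs.** From the documents: 33 per arm, two-sided 0.05, the two bands, 14 post-baseline readings. Assumed: normal rates, SD 4 or 5, a constant true fall of 3 breaths/min, control means 20, 22 and 24. The no-escalation condition, early stopping of data collection and the Bonferroni correction for pairwise comparisons are left out.

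**One reading, means.** Noncentrality = 3 / (SD × √(2/33)). For SD 4 this is 3/(4 × 0.246) = 3.05, and power on 64 df is 0.85. For SD 5 it is 2.44, and power is 0.67.

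**One reading, band.** In-band share = Φ((U + 0.5 − μ)/SD) − Φ((11.5 − μ)/SD), with U = 20 or 29. For U = 20, SD 4 and μ = 20: Φ(0.125) − Φ(−2.125) = 0.533. For μ = 17: Φ(0.875) − Φ(−1.375) = 0.725. At SD 4:

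| Control mean | 12-20, control → NHF | 12-29, control → NHF |
|---|---|---|
| 20 | 53.3% → 72.5% | 97.4% → 91.5% |
| 22 | 34.9% → 61.6% | 96.5% → 96.5% |
| 24 | 19.0% → 44.1% | 91.5% → 97.4% |

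Power for each pair of shares is from the exact Fisher test.

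**Fourteen readings.** With within-patient correlation ρ = 0.5, the SD of a patient's mean is SD × √((1 + 13ρ)/14) = SD × √(7.5/14) = 0.732 × SD. For the bands, each patient's proportion of in-band readings is compared between arms, as a stand-in for the planned logistic regression.

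| | SD 4: means | 12-20 | 12-29 | SD 5: means | 12-20 | 12-29 |
|---|---|---|---|---|---|---|
| One reading | 0.85 | 0.29-0.53 | 0.00-0.03 | 0.67 | 0.14-0.30 | 0.01-0.06 |
| 14 readings, ρ = 0.5 | about 0.98-0.99 | 0.84-0.97 | 0.04-0.60 | about 0.90 | 0.55-0.83 | 0.04-0.41 |

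For 12-29 at a control mean of 20, the in-band share falls in the NHF arm, so a significant result there would favour control.

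**Lower control means.** At SD 5, one reading, by the normal approximation, the 12-20 band has power 0.10 at a control mean of 16 and 0.04 at 18. Means have 0.68 by the same approximation.

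**Direction.** Under normality the in-band share falls when the average of the two group means lies below the band's midpoint. For 12-20 that is (11.5 + 20.5)/2 = 16. For 12-29 it is (11.5 + 29.5)/2 = 20.5, so with a fall of 3 the effect cancels at a control mean of 22 and reverses below it. Example for 12-20, SD 5: control mean 16 falling to 13 takes the share from 63% to 55%.

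**Wider range.** Over control means 16-24, SD 4-6 and falls of 2-4, on one reading, the band had less power than means in 45 of 45 scenarios for each band, with normal and with lognormal rates. The median loss was 30 to 40 points. The share fell in 9 (normal) or 11 (lognormal) of 45 scenarios for 12-20, and in 30 or 26 of 45 for 12-29.

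**The case against.** **The planned analysis uses all readings.** From the single-reading figures a reader might infer that the trial has little chance of showing a lower rate. That does not follow for the band the Statistical Analysis Plan names: with 14 readings it still reaches 0.84-0.97 at SD 4. The result depends on the assumed correlation. Over ρ = 0.3 to 0.7 and both SDs, the 12-20 band runs from about 0.4 to above 0.99. This objection stands, and it limits the size of the point.

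**A benefit scored as harm.** A reader might also infer that the plan would count an NHF benefit against NHF. For 12-20 at control means of 20-24 the direction is always right. Reversal comes from rates below 12, which the protocol places outside its own ranges for the breathing trial and for weaning. Whether such a rate is a benefit is a clinical judgement that the documents do not settle. What stands is arithmetic: a downward shift can cancel out or lower the in-band share.

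**Starting inside the band.** It is tempting to say that everyone starts inside 12-29, because Methods requires "respiratory rate: 12-29 breaths/min". That is a criterion of the T-piece trial before extubation. Study baseline comes after extubation, and nothing guarantees the rate is still in range.

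**The outcome is maintenance, not mean rate.** True: the binary analysis follows the declared secondary outcome, and the order of items in the Aim sets no priority. The methods summary placed before Study Eligibility Criteria also allows escalation to keep the rate within 12-29, so a mixed model alone would credit a rate brought down by extra support. This is a good reason to keep the maintenance outcome and add to it. It is not a reason to leave the rate unanalysed as a number.

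**Conclusion.** The point holds as a loss of efficiency in a secondary comparison. The primary analysis and the sample size are untouched. The loss is moderate for 12-20 at control means of 20-24, larger at 16-18, and severe for 12-29. That means are more powerful than the band held in every scenario tried. The amounts depend on assumed means, SDs, effect and correlation, and the calculation leaves out the no-escalation condition. The Bonferroni correction would lower the power of both approaches.

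The conflict between the two bands is a separate defect, but it decides how much is lost. Reconciling it would not remove the need for a numeric analysis, because both bands lose power.

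**What to change.** In the Statistical Analysis Plan, add respiratory rate in breaths/min to the linear mixed models already specified (group, time, group by time, patient as random factor) as a prespecified secondary comparison between arms. Report it alongside the maintenance outcome, not in place of it.

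Add a sensitivity analysis for two features of the data: readings taken under escalated support, and the end of four-hourly collection at mechanical ventilation or ICU discharge (Treatment decisions and premature discontinuation of physiological data collection). Those two exits carry opposite prognoses and should not be handled as one kind of missing data.

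Keep the maintenance composite as it is built, and reconcile its respiratory-rate band between Outcome measures (12-29) and the Statistical Analysis Plan (12-20).

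The cost is one more model with its sensitivity analysis and one more secondary P value. No new measurement is needed. Prespecifying the model also avoids a later choice between the numeric and the banded result in an unblinded trial.
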